Diagnosis and Main Inclusion Criteria	Stage III, IVa, or IVb squamous cell carcinoma of the oral cavity, oropharynx, larynx, or hypopharynx with ECOG performance status 0-2
Study Product, Dose, Route, Regimen	
Nelfinavir (Viracept®) 1250 mg By mouth two times a day Medicine should be taken with food, preferably high in fat.
 
¹⁸F-FMISO 5-10 mCi Intravenous bolus injection

Duration of administration	Treatment to start 7-14 days prior to radiation and continued throughout radiation and standard chemotherapy.
Reference therapy	Combination of standard chemotherapy and radiation therapy
Statistical Methodology	This is a single arm, phase II study of nelfinavir (1250 mg given po bid) and concurrent chemoradiotherapy in locally advanced head and neck cancer. Locoregional control will be compared to published historical results. There will be a total of 28 patients enrolled on the study.

1 Introduction

This is a Phase II trial of definitive chemoradiotherapy (CTRT) given with the protease inhibitor, Nelfinavir (NFV), in patients with locally advanced head and neck cancer. Eligible patients will receive a “lead-in” period of Nelfinavir (1250 mg po bid) for 7-14 days prior to initiation of CTRT. Nelfinavir will then be given concurrently with platinum-based chemotherapy and radiation therapy (planned total dose of 70 Gy over 7 weeks).

All patients will also undergo the following:

- 1) ^{18}F -FMISO PET/CT: this scan assesses tumor hypoxia. Patients will undergo 2 separate ^{18}F -FMISO PET/CT scans: the first at baseline to determine baseline tumor hypoxia, the second after a 7-14 day lead-in of NFV prior to CTRT (to determine change in tumor oxygenation secondary to NFV). Six patients will receive 3 separate ^{18}F -FMISO PET/CT, the first at baseline to determine baseline tumor hypoxia, the second also at baseline to determine reliability of the scan for test-retest purposes, the third after a 7-14-day lead-in of NFV.
- 2) ^{18}F -FDG PET/CT: this scan assesses glucose uptake. Patient will undergo 2 separate ^{18}F -FDG PET/CT scans: the first at baseline as part of routine clinical care, for purposes of radiation treatment planning and the second after a 7-14 day lead-in of NFV prior to CTRT (to determine change in tumor glucose uptake secondary to NFV).

The primary objective of the study will be to determine whether NFV, given with definitive CTRT, will improve locoregional control in locally advanced head and neck cancer.

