In the current protocol we focus on the central hypothesis that NFV will result in a decrease in tumor hypoxia in head and neck tumors, and that this alteration in hypoxia plays a role in its ability to radiosensitize, leading to improved treatment outcomes. We also hypothesize that: 1) the effect of NFV on hypoxia can be assessed by ^{18}F -EF5 or by ^{18}F -FMISO,(the initial 15 subjects have been completed using ^{18}F -EF-5) and 2) changes in hypoxia will correlate with changes in glucose metabolism (decrease in glucose uptake), as assessed by ^{18}F -FDG PET/CT scanning.

Summary

We propose a clinical trial of the HIV protease inhibitor, nelfinavir, and concurrent, definitive chemoradiation in patients with locally advanced, HPV-negative head and neck cancer. This is an ideal population because of their poor prognosis with current therapy and the fact that HNSCC tumors are known to be hypoxic. Furthermore, activation of the EGFR/PI3K pathway is common in HNSCC, identified in 74% of cases in one report (30), so these tumors should respond to NFV. Assessment of tumor oxygenation response to NFV will be made using ^{18}F -FMISO PET/CT scanning and correlation of hypoxia with glucose metabolism will be assessed via ^{18}F -FDG PET/CT scanning. If the combination of NFV and radiation is found to be effective in this group of patients, it could then be extended to patients with other cancers.

2 Study Objectives

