3.1 General Design

Twenty-eight subjects will be enrolled on this clinical trial investigating the efficacy of definitive NFV + CTRT for locally advanced head and neck cancer. Patients will also receive two ¹⁸F-FMISO PET/CT studies: the first at baseline to determine baseline tumor hypoxia, the second after a 7-14 day lead-in of NFV prior to CTRT (to determine change in tumor oxygenation secondary to NFV). Additionally, patients will undergo 2 separate ¹⁸F-FDG PET/CT scans: the first at baseline as part of routine clinical care, for purposes of radiation treatment planning and the second after a 7-14 day lead-in of NFV prior to CTRT (to determine change in tumor glucose uptake secondary to NFV). The research ¹⁸F-FMISO PET/CT and ¹⁸F-FDG PET/CT studies are **mandatory**, in order to participate on this clinical trial. Only under circumstances where the PI, [name], deems the patient is unable to comply with the PET/CT requirements will its completion be excused and allow the patient to remain on the study.

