6.3 Chemotherapy Administration

Standard cisplatin chemotherapy consisting of cisplatin will be administered as concurrent therapy with radiation. Cisplatin 100 mg/m² will be administered on days 1, 22, and 43, with pretreatment and post treatment hydration and a polyantiemetic regimen. Patients may also be treated with either weekly cisplatin or weekly cetuximab, which is another FDA-approved drug shown to be an effective radiosensitizer in the treatment of head and neck cancer (36, 37).

Patients who are receiving cetuximab may receive a loading dose, as per standard of care, prior to their completion of their repeat imaging, if deemed necessary by the treating physician. The treating medical oncologist may make adjustments to the chemotherapy regimen and/or dosing, as they deem medically appropriate. Development of severe dysphagia, dehydration, orthostasis, or other unforeseen grade 4 toxicity is potential grounds for discontinuation of treatment if therapy is delayed longer than 1 week to permit recovery. Should a holiday or hospital closing interfere with the above detailed chemotherapy administration schedule, the medical oncologist will adjust each subjects administration as they see medically appropriate.

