6.4 Radiation Therapy

Radiation therapy in all subjects will begin 7 to 14 days after the initiation of nelfinavir.

Simulation for treatment is required. PET/CT-based treatment planning is required. Treatment will be delivered via intensity-modulated photon or pencil-beam proton radiotherapy. All fields will be treated every session. Interruptions in therapy should be discussed with the principal investigator but will be instituted at the discretion of the attending radiation oncologist.

The gross tumor volume, clinical treatment volume, and planning treatment volume are defined according to ICRU 50. Dose calculation should be performed using inhomogeneity corrections to account for differences in tissue density across the head and neck region. The total dose to gross disease will be 70 Gy. This will be administered in 2.0 Gy daily fractions. Regional lymph node regions may be treated, as dictated by the clinical situation. High-risk elective nodal regions would receive anywhere from 59.5 to 63 Gy, administered in 1.7-1.8 Gy daily fractions, while low-risk elective nodal regions would receive anywhere from 56 to 59.5 Gy, administered in 1.6- 1.7 Gy daily fractions. Treatment will be continuous, 5 days per week for 7 consecutive weeks.

Normal tissue doses: Dose-volume histograms should be performed for organs at risk, such as the spinal cord, brainstem, optic nerves and chiasm, pharyngeal constrictors, and mandible. The

maximal spinal cord dose should not exceed 45 Gy. The maximal dose to the brainstem, optic nerves and chiasm, should not exceed 54 Gy. The mean dose to the pharyngeal constrictors should not exceed 50 Gy. The maximal dose to the mandible (not included in the planning treatment volume) should not exceed 70 Gy.

6.5 ¹⁸F-FMISO PET/CT Imaging

Two ¹⁸F-FMISO PET/CT imaging scans to assess tumor oxygen level in response to treatment with Nelfinavir will be performed. Pregnancy tests will be performed prior to each scan. The first ¹⁸F-FMISO PET/CT will occur shortly after enrollment, prior to administration of any therapy. The second will occur after a 7-14 day period of NFV alone.

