6.9 Study Visit Flowchart

7 Statistical Plan

A 28 patient phase II trial of NFV and concurrent chemo/RT with measurements of hypoxia by $^{18}\text{EF-5}$ or FMISO PET imaging and serum biomarkers will be performed. Locoregional control is the primary endpoint, defined from first day of chemo/RT+NFV to local or regional progression. Distant progression and patients free of locoregional control will be censored. The "pre and post-NFV" measurements mentioned below, refer to samples obtained before and after a 7-14 day run-in period of NFV prior to chemo/RT. These pre/post-NFV changes are evaluated as "early change" predictors of treatment outcome. Hypotheses tested by statistical analyses are:

NFV given with chemo/RT will improve locoregional control (primary objective) will be tested by comparing our locoregional control to a historical result by log rank test with adequate power as described below. In a randomized pilot study by Rischin (JCO 24:2098-2104, 2006) in head and neck cancer, patients with hypoxic tumors who received concurrent chemoradiotherapy had a 3-year locoregional control rate of 30%, while patients who received the hypoxia-activating pro-drug tirapazamine and concurrent chemoradiotherapy had a 3-year locoregional rate of 95%. Although the difference in local control was stunning, the sample sizes of these groups was very modest. Therefore, we have powered our study conservatively, in order to detect a more modest treatment effect.

Starting with this amendment, a total of 28 patients will be enrolled over 4 years, assuming a rate of 7 patients per year. To date, only 2 larynx cancer patient had been enrolled on this trial, so 4 years of accrual will be needed to meet the target sample size. We will then follow patients for an additional 6 months. There will be 85% power to detect a 30% absolute increase in 3-year locoregional control from a 40% rate for standard concurrent chemoradiotherapy to 70% for Nelfinavir and concurrent chemoradiotherapy, using a 1-sided log rank test at a 5% type I error rate. Power calculated with SWOG software (http://www.swogstat.org/stat/public/one_nonparametric_survival.htm).

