NFV will reduce tumor hypoxia will be tested by comparing pre and post-NFV hypoxia (i.e., $^{18}\text{EF-5}$ uptake expressed as a tumor to muscle (TMR) ratio) by Student's paired t-test. Transformation of the ratio may be necessary in order to meet the normality assumption of the t-test. Assuming an effect size (δ), in units of Std Dev of differences ($\delta = |\mu_d|/\sigma_d$), of $1/2\sigma_d$, with 28 patients enrolled there is 82% power to detect the difference between pre/post-NFV values using a 1-sided paired t-test at a stricter 5% type I error, used to control false positive conclusions in our correlative analyses.

Baseline hypoxia, and glucose uptake are predictive of treatment outcome will be tested by an exploratory analysis using Cox regression. Each variable will be tested in a univariate survival model to assess association with locoregional control. The hazard ratio, 95% confidence interval and statistical significance will be determined for each variable. Exploratory analyses will also evaluate differences between Nelfinavir responders and nonresponders. The definition of "NFV responder" requires greater knowledge about the distribution and variance of the baseline TMR. For example, a decrease in TMR to <1.25 or percent decrease from baseline of $>50\%$ may be reasonable definitions. This exploratory analysis yields estimates of treatment outcomes within response groups.

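### Cetuximab may be loaded before the repeat scan, against the NFV-alone condition, and no rule covers loaded patients in the pre/post hypoxia test

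*Combined protocol and SAP*

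**What the plan says.** Section 6.3 names cisplatin first as the concurrent drug and allows weekly cisplatin or weekly cetuximab instead. It sets no cap on cetuximab and gives no expected share. It then states: "Patients who are receiving cetuximab may receive a loading dose, as per standard of care, prior to their completion of their repeat imaging", with the qualifier "if deemed necessary by the treating physician".

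Section 6.5 says of the two hypoxia scans: "The second will occur after a 7-14 day period of NFV alone". Sections 3.1 and 6.1 likewise treat the change between scans as the consequence of NFV.

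Section 7 defines the paired measurements as those taken "before and after a 7-14 day run-in period of NFV prior to chemo/RT" and tests whether NFV reduces hypoxia: "with 28 patients enrolled there is 82% power to detect the difference between pre/post-NFV values using a 1-sided paired t-test". The assumed effect is half a standard deviation of the differences, at a 5% one-sided level. Section 7 gives no imaging analysis population and no exclusion, covariate or sensitivity analysis for patients loaded before scan 2. The only imaging exception is in section 3.1, where a patient may stay on study without the scans if the PI "deems the patient is unable to comply with the PET/CT requirements will its completion be excused". That does not concern cetuximab.

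The background (section 1.1) calls this question the "central hypothesis that NFV will result in a decrease in tumor hypoxia in head and neck tumors". The Study Summary confirms there is no comparator: "This is a single arm, phase II study of nelfinavir".

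**The concern.** A scan taken after a cetuximab dose cannot also be a scan taken after NFV only. The conflict is between two current operating rules, not a matter of missing detail: one permits what the other says will not happen.

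There is no control arm to absorb the effect of a second drug started between the scans. For a loaded patient, the change in tumor to muscle ratio (TMR) reflects NFV plus cetuximab, and section 6.3 itself describes cetuximab as an effective radiosensitizer. Two analysts could defensibly treat such patients differently, and could choose after seeing the data.

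At stake is a secondary endpoint, though one that tests the proposed mechanism. The exploratory responder comparison could also be touched, by an amount that cannot be sized because the responder definition is not fixed.

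**Working it through.** **Inputs from section 7.** n = 28, effect d = 0.5 SD of the paired differences, one-sided alpha = 0.05, stated power 82%.

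**Inputs not in the documents (assumed).** k = number loaded before scan 2, taken as 1, 2, 3, 5 or 7. c = cetuximab shift in TMR change, in SD units, taken as 0.25 or 0.5. The range stops at 0.5 because that is the effect the plan assumes for NFV itself.

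**Step 1: the plan's own figure.** Paired t-test, 27 df, critical value 1.703, noncentrality 0.5 × √28 = 2.646. Power from the noncentral t is 82.5%, so the stated 82% is correct.

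**Step 2: effect of pooling loaded patients when NFV does nothing.** The mean change moves by k × c / 28; for k = 3, c = 0.5 this is 1.5 / 28 = 0.054 SD. Rejection rates come from simulation: 400,000 runs per cell, unit-SD differences, shift in k patients only, in the direction of lower TMR.

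| k of 28 | Mean shift at c = 0.5 | Error at c = 0.25 | Error at c = 0.5 |
|---|---|---|---|
| 1 | 0.018 SD | 5.5% | 5.9% |
| 2 | 0.036 SD | 6.0% | 7.0% |
| 3 | 0.054 SD | 6.5% | 8.3% |
| 5 | 0.089 SD | 7.7% | 11.2% |
| 7 | 0.125 SD | 9.2% | 15.0% |

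The test in the 28 − k unloaded patients rejects 5.0% at every k, given no other source of change.

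**Step 3: NFV truly works (0.5 SD).** Power of the unloaded-patient test uses noncentrality 0.5 × √(28 − k). The other columns are all-scanned power when cetuximab pushes the opposite way.

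| k | Unloaded n | Unloaded power | All scanned, opposing 0.25 SD | All scanned, opposing 0.5 SD |
|---|---|---|---|---|
| 3 | 25 | 78.3% | 78.5% | 74.0% |
| 5 | 23 | 75.1% | 75.7% | 67.1% |
| 7 | 21 | 71.5% | 72.6% | 59.8% |

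At an opposing 0.25 SD, restriction gains no power. With 1 or 2 excluded, unloaded power is 81.2% or 79.8%.

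**Step 4: what restriction does not remove.** Suppose every patient drifts down by 0.1 SD for reasons unrelated to either drug. Noncentrality is 0.1 × √n, and rejection with no NFV effect is 12.9% at n = 28 and 12.3% at n = 25. Leaving out loaded patients hardly changes it.

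**Step 5: hypoxia-FDG correlation.** With c = 0.5 on both changes, otherwise independent, and k = 3, 5 or 7 (200,000 runs), the spurious mean r is at most 0.05 in size. A two-sided 5% test (sidedness assumed) rejects in 5.1-5.6%.

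**The case against.** The strongest reply is that the size is wholly assumed. Bias needs a patient on cetuximab rather than cisplatin, a physician who judges early loading necessary, and a dose that actually precedes scan 2. k may be zero, and no document supports 5 or 7. Nor do the documents say cetuximab alters FMISO or EF5 uptake. This stands: the figures are conditional, and at 1-3 loaded they are small.

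Second, section 7 places the run-in before chemo/RT. If a loading dose counts as starting chemotherapy, a post-loading scan already falls outside the defined measurement. That is a fair reading, so a reader should not infer that loaded scans will certainly be pooled. But section 6.3 expressly foresees such scans and nothing says they are left out, so the gap remains.

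Third, a reader might infer that the unloaded-patient test isolates the NFV effect. It does not. Regression to the mean and spontaneous change stay in any uncontrolled pre/post comparison, and step 4 shows that a modest drift outweighs the k = 3 contamination. This stands and limits what the fix can claim.

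Fourth, sections 3.2 and 3.3 say the first 15 subjects were imaged with EF5. The simulation treats all 28 differences as alike, and a rule written now is partly retrospective for those already scanned. Both are true, but neither removes the need for a rule.

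Fifth, if cetuximab does not affect uptake, restriction costs power for no gain in error control. That is a reason to report both analyses, not to leave the choice open.

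**Conclusion.** The point holds in a limited form. Sections 6.3 and 6.5 conflict, section 7 does not say how loaded patients are analysed, and in each such patient the secondary hypoxia change mixes two active drugs. The amount of bias is unknown. Under the assumed 0.5 SD cetuximab reduction and no NFV effect, the nominal 5% error is about 6-8% for 1-3 loaded and 11-15% for 5-7; at 0.25 SD it is between 5.5% and 9.2% over the whole range. If nobody is loaded before scan 2, there is no bias from this source.

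Stronger readings are not supported. The stated power is not wrong. The primary locoregional control test does not use the scans and is unaffected. The hypoxia-FDG correlation is barely moved and needs no restricted version. The documents do not show that the hypoxia result will be wrong, only that one avoidable confounder is permitted and unhandled. It should be corrected; confidence is medium because the number loaded is not known.

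**What to change.** 1. Reconcile 6.3 with 6.5, so that 6.5 acknowledges the loading exception. The physician's freedom to load need not change.
2. Record the date of any cetuximab or chemotherapy dose relative to scan 2, and report how many patients were dosed before it.
3. Pre-specify the paired hypoxia t-test in patients whose second scan preceded any such dose, which is the condition 6.5 describes, and report it beside the result in all scanned patients.
4. Do not describe the change as due to NFV alone if the two disagree. Say in advance what counts as disagreement, preferably from the estimates and their intervals: requiring both tests to be significant gives power of only 76%, 73% or 69% for 3, 5 or 7 loaded, even if cetuximab has no effect.
5. State in the report that this removes one confounder and does not by itself establish causation.

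**Cost.** Analysis-plan wording, plus dose and scan dates if not already captured (the case report form is not in the documents). Power of the restricted test at 0.5 SD falls from 82% to about 78%, 75% or 72% with 3, 5 or 7 excluded. Because loading follows clinical judgement, the restricted result applies to patients not selected for early loading. If no one is loaded, the two analyses coincide.

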6.4 Radiation Therapy

Radiation therapy in all subjects will begin 7 to 14 days after the initiation of nelfinavir.

Simulation for treatment is required. PET/CT-based treatment planning is required. Treatment will be delivered via intensity-modulated photon or pencil-beam proton radiotherapy. All fields will be treated every session. Interruptions in therapy should be discussed with the principal investigator but will be instituted at the discretion of the attending radiation oncologist.

The gross tumor volume, clinical treatment volume, and planning treatment volume are defined according to ICRU 50. Dose calculation should be performed using inhomogeneity corrections to account for differences in tissue density across the head and neck region. The total dose to gross disease will be 70 Gy. This will be administered in 2.0 Gy daily fractions. Regional lymph node regions may be treated, as dictated by the clinical situation. High-risk elective nodal regions would receive anywhere from 59.5 to 63 Gy, administered in 1.7-1.8 Gy daily fractions, while low-risk elective nodal regions would receive anywhere from 56 to 59.5 Gy, administered in 1.6- 1.7 Gy daily fractions. Treatment will be continuous, 5 days per week for 7 consecutive weeks.

Normal tissue doses: Dose-volume histograms should be performed for organs at risk, such as the spinal cord, brainstem, optic nerves and chiasm, pharyngeal constrictors, and mandible. The

maximal spinal cord dose should not exceed 45 Gy. The maximal dose to the brainstem, optic nerves and chiasm, should not exceed 54 Gy. The mean dose to the pharyngeal constrictors should not exceed 50 Gy. The maximal dose to the mandible (not included in the planning treatment volume) should not exceed 70 Gy.

6.5 ¹⁸F-FMISO PET/CT Imaging

Two ¹⁸F-FMISO PET/CT imaging scans to assess tumor oxygen level in response to treatment with Nelfinavir will be performed. Pregnancy tests will be performed prior to each scan. The first ¹⁸F-FMISO PET/CT will occur shortly after enrollment, prior to administration of any therapy. The second will occur after a 7-14 day period of NFV alone.

The ¹⁸F-FMISO PET/CT study will be conducted at the Imaging Services Center located in the Department of Radiation Oncology, Perelman Center for Advanced Medicine, University of Pennsylvania Medical Center. Subjects will receive ¹⁸F-FMISO intravenously over a period of approximately a minute. Subjects will then lie on a table under the PET scanning machine for the procedure. The following is a timetable for the ¹⁸F-FMISO PET/CT scan.

TIME (APPROXIMATELY)	SCHEDULE OF EVENTS
30 minutes before injection	Arrival at nuclear medicine facility, intravenous line placed: weight taken
0 minutes	Intravenous injection of [F18]-FMISO (5-10 mCi)
10 min prior to imaging	Empty Bladder
2-3 hours after injection	[F18]-FMISO PET/CT scan of the head and neck
20 min of imaging	Study Visit Complete

6.6 FDG PET/CT Imaging

Two ¹⁸F-FDG PET/CT imaging scans will be performed. The first is part of routine clinical care, and for purposes of radiation treatment planning, the second is for research purposes, in order to determine the effect of NFV on glucose uptake.

The ¹⁸F-FDG PET/CT study will be conducted at the Imaging Services Center located in the Department of Radiation Oncology, Perelman Center for Advanced Medicine, University of Pennsylvania Medical Center. S

